7 TRIAL PROCEDURES

7.1 Trial Procedures

The [Trial Flow Chart - Section 6](#) summarizes the trial procedures to be performed at each visit. Individual trial procedures are described in detail below. It may be necessary to perform these procedures at unscheduled time points if deemed clinically necessary by the investigator.

Furthermore, additional evaluations/testing may be deemed necessary by the Sponsor for reasons related to subject safety. In some cases, such evaluation/testing may be potentially sensitive in nature (e.g., HIV, hepatitis C, etc.), and thus local regulations may require that additional informed consent be obtained from the subject. In these cases, such evaluations/testing will be performed in accordance with those regulations.

7.1.1 *Administrative Procedures*

7.1.1.1 *Informed Consent*

The Investigator must obtain documented informed consent from each potential subject prior to participating in a clinical trial.

7.1.1.1.1 **General Informed Consent**

Consent must be documented by the subject's dated signature on a consent form along with the dated signature of the person conducting the consent discussion.

A copy of the signed and dated consent form should be given to the subject before participation in the trial.

The initial informed consent form, any subsequent revised written informed consent form and any written information provided to the subject must receive the IRB/ERC's approval/favorable opinion in advance of use. The subject should be informed in a timely manner if new information becomes available that may be relevant to the subject's willingness to continue participation in the trial. The communication of this information will be provided and documented via a revised consent form or addendum to the original consent form that captures the subject's dated signature.

Specifics about a trial and the trial population will be added to the consent form template at the protocol level.

The informed consent will adhere to IRB requirements, applicable laws and regulations and Sponsor requirements.

7.1.1.2 *Inclusion/Exclusion Criteria*

All inclusion and exclusion criteria will be reviewed by the Investigator or qualified designee to ensure that the subject qualifies for the trial.

7.1.1.3 *Subject Identification Card*

All subjects will be given a Subject Identification Card identifying them as participants in a research trial. The card will contain trial site contact information (including direct telephone numbers) to be utilized in the event of an emergency. The Investigator or qualified designee will provide the subject with a Subject Identification Card after the subject provides written informed consent.

7.1.1.4 *Medical History*

A medical history will be obtained by the Investigator or qualified designee. Medical history will include all active conditions, and any condition diagnosed within the prior 10 years that are considered to be clinically significant by the Investigator. Details regarding the disease for which the subject has enrolled in this study will be recorded separately and not listed as medical history.

7.1.1.5 *Surgical History*

A surgical history will be obtained by the investigator or qualified designee. Surgical history will include all clinically relevant surgeries including, but not limited to artificial (prosthetic) joints, implants and/or devices, such as ports or stents. Surgical procedures that occur after study enrollment will be documented separately.

7.1.1.6 *Prior and Concomitant Medications Review*

7.1.1.6.1 *Prior Medications*

The investigator or qualified designee will review and record prior medication use, including any protocol-specified washout requirement, and record prior medication taken by the subject within 28 days before informed consent is signed. Treatment for the disease for which the subject has enrolled in this study will be recorded separately and not listed as a prior medication. In addition, all prescription and nonprescription medication (excluding vitamins and nutritional supplements) taken by the subject from 28 days prior to signing informed consent and up to and including 30 days after the last administration of ADXS31-142, if any, should be recorded in the eCRF. All medications related to reportable SAEs will be recorded in the medical record and on the CRF. Any addition, deletion, or change in the dose of these medications will also be recorded. Generic names should be used to eliminate confusion that may result from trade names. Protocol-mandated prophylactic medications and antibiotics should also be captured in the CRF along with any addition.

7.1.1.6.2 Concomitant Medications

The Investigator or qualified designee will record medication, if any, taken by the subject during the trial. All medications related to reportable SAEs and ECIs should be recorded as defined in [Section 7.2](#).

7.1.1.6.3 Non-Drug Treatment/Procedures

The Investigator or qualified designee will document any non-drug treatment or surgical procedures. All treatments/procedures related to reportable AE/SAEs and ECIs should be recorded as defined in [Section 7.2](#).

7.1.1.7 *Disease Details and Treatments*

7.1.1.7.1 Prior Cancer History

The Investigator or qualified designee will obtain prior and current details regarding disease status.

7.1.1.7.2 Prior Cancer Treatment

The Investigator or qualified designee will review all prior cancer treatments including systemic treatments, radiation and surgeries.

7.1.1.7.3 Subsequent Anti-Cancer Therapy Status

The Investigator or qualified designee will review all new anti-neoplastic therapy initiated after the last dose of trial treatment. If a subject initiates a new anti-cancer therapy within 30 days after the last dose of trial treatment, the 30-day Safety Follow-up visit must occur before the first dose of the new therapy. Once new anti-cancer therapy has been initiated the subject will move into follow-up.

7.1.1.8 *Assignment of Subject Identification Number*

After giving signed informed consent, subjects will be assigned a unique number to be used as identification throughout the trial.

7.1.2 *Clinical Procedures/Assessments*

7.1.2.1 *Adverse Event (AE) Monitoring*

The Investigator or qualified designee will assess each subject to evaluate for potential new or worsening AEs/SAEs from the time written informed consent is obtained through the completion of the 30-Day follow-up. Adverse events and SAEs experienced during this period will be reported and recorded in the eCRF. Adverse experiences will be graded and recorded throughout the study and during the follow-up period according to

CTCAE v 4.03 (Refer to [Section 12.2](#)). Toxicities will be characterized in terms of seriousness, causality, toxicity grading, and action taken with regard to study treatment.

Please refer to [Section 7.2](#) for detailed information regarding the assessment and recording of AEs.

7.1.2.2 *Physical Examination*

[figure not shown]
The Investigator or qualified designee will perform a complete physical examination during the screening period. Clinically significant abnormal findings should be recorded as medical history. Clinically significant abnormal findings noted during the treatment period should be recorded as an AE. A physical examination should also be performed before each treatment administration and at the end of therapy as specified in the Trial Flow Chart ([Section 6](#)).

7.1.2.3 *Vital Signs*

The Investigator or qualified designee will take vital signs at screening, prior to the administration of each dose of trial treatment, every [REDACTED] for [REDACTED] following each ADXS31-142 dose, and at treatment discontinuation as specified in the Trial Flow Chart ([Section 6](#)). Vital signs should include temperature, pulse, respiratory rate, weight and blood pressure. Height will be measured at screening only. During Part B, weight will be collected once at every visit.

7.1.2.4 *Eastern Cooperative Oncology Group (ECOG) Performance Scale*

The Investigator or qualified designee will assess ECOG status (see [Section 12.1](#)) at screening, prior to the administration of each dose of trial treatment and discontinuation of trial treatment as specified in the Trial Flow Chart ([Section 6](#)).

7.1.2.6 *Tumor Imaging and Assessment of Disease*

Computed tomography (CT), magnetic resonance imaging (MRI) or bone scan will be considered the best currently available and reproducible methods to measure target lesions (as defined in [Section 7.1.2.5.2](#)) selected for response assessment. Conventional CT and MRI of the abdomen/pelvis should be performed with contiguous cuts of 10 mm or less. Spiral CT scan should be performed using a 5 mm contiguous reconstruction algorithm (as a general rule, lesion diameter should be no less than double the slice thickness). Lesions on chest x-rays will be acceptable as measurable lesions when they are clearly defined and surrounded by aerated lung; however, CT is preferable.

Ultrasound will not be an acceptable method to measure disease. Bone scan response assessment will be primarily based on the PCWG2 criteria. [\[38\]](#)

7.1.2.6.1 *Measurable and Non-measurable Lesions and Disease*

Measurable lesions will be those that can be accurately measured in at least one dimension with the longest diameter ≥ 10 mm (for spiral CT scan or MRI scan, ≥ 5 mm). Measurable disease will be present if the subject has 1 or more measurable lesions.

Non-measurable lesions/disease will be all other lesions (or sites of disease), including small lesions (those with all measurements <10 mm with spiral CT or <5 mm with MRI), or any of the following: bone lesions, leptomeningeal disease, ascites, pleural or pericardial effusion, lymphangitis, cutis/pulmonis, abdominal masses that are not confirmed and followed by imaging techniques, cystic lesions, and lesions occurring within a previously irradiated area unless they are documented as new lesions since the completion of radiation therapy.

7.1.2.6.2 *Target/Non-Target Lesions*

All measurable lesions, up to a maximum of 2 lesions per organ and 5 lesions in total, should be identified as target lesions to be measured and recorded at baseline. The target lesions should be representative of all involved organs. Target lesions will be selected based on their size (the lesion with the longest diameter) and suitability for accurate repeated measurements. At baseline, a sum of the longest diameters for all target lesions will be calculated and recorded as the baseline tumor burden. The baseline sum will be used as the reference point to determine the objective tumor response of the target lesions.

Measurable lesions other than the target lesions and all sites of non-measurable disease will be identified as non-target lesions and will be recorded at baseline. Non-target lesions will be evaluated at the same time points as target lesions.

7.1.2.6.3 Response in Measurable Lesions (RECIST 1.1)

At baseline, the sum of the longest diameters (SumD) of all target lesions (up to 2 lesions per organ, up to total 5 lesions) is measured. At each subsequent tumor assessment (TA), the SumD of the target lesions and of new, measurable lesions are added together to provide the total measurable tumor burden (TMTB):

TMTB = SumD target lesions + SumD new, measurable lesions

Percentage changes in TMTB per assessment time point describe the size and growth kinetics of both old and new measurable lesions as they appear. At each TA, the response in target and new measurable lesions is defined based on the change in TMTB (after ruling out irPD) as follows:

- Complete Response (CR): disappearance of all target lesions. Any pathological lymph nodes (whether target or non-target) must have reduction in short axis to ≤ 10 mm.
- Partial Response (PR): At least a 30% decrease in sum of diameter of target lesions, taking as reference the baseline sum diameter.
- Stable Disease (SD): Neither sufficient shrinkage to qualify for PR nor sufficient increase to qualify for PD, taking as reference the smallest sum diameters while on study.
- Progressive Disease (PD): At least a 20% increase in the sum of diameters of target lesions, taking as reference the smallest sum on study (this includes the baseline sum if that is the smallest on study). In addition to the relative increase of 20%, the sum must also demonstrate an absolute increase of at least 5 mm. (Note: the appearance of one or more new lesions is also considered progression).

7.1.2.6.4 Immune-Related Response in Measurable Lesions (irRECIST)

In addition to evaluation using RECIST 1.1 criteria, an immune response adaptation of RECIST will be applied to this trial. The essential differences between irRECIST and RECIST criteria are as follows:

- New measurable lesions do not necessarily constitute progressive disease and they should be added into the total tumor burden. New non-measurable lesions do not constitute disease progression but will prevent the determination of an irCR.
- Subjects with an initial finding of progressive disease (irPD) before or at the 12-week imaging assessment, but without rapid clinical deterioration, require confirmation of irPD with a second, consecutive scan obtained ≥ 4 weeks from the

initiation documentation. Subjects will continue to receive study treatment until irPD is confirmed at this later time point.

At baseline, the sum of the longest diameters (SumD) of all target lesions (up to 2 per organ and 5 in total) is measured. At each subsequent tumor assessment, the SumD of the target lesions and of new, measurable lesions (≥ 10 mm [lymph nodes ≥ 15 mm in shortest diameter]; up to 2 new lesions per organ, total 5 new lesions) are added together to provide the total measurable tumor burden (TMTB):

$$\text{TMTB} = \text{SumD target lesions} + \text{SumD new, measurable lesions}$$

Percentage changes in TMTB per assessment timepoint describe the size and growth kinetics of both old and new measurable lesions as they appear. At each tumor assessment, the response in target and new measurable lesions is defined based on the change in TMTB (after ruling out irPD) as follows:

- Complete Response (irCR): complete disappearance of all target and new, measurable lesions, with the exceptions of lymph nodes which must decrease to <10 mm in short axis
- Partial Response (irPR): decrease in TMTB $\geq 30\%$ relative to baseline (see below)
- Stable Disease (irSD): not meeting criteria for irCR or irPR, in absence of irPD
- Progressive Disease (irPD): increase in TMTB $\geq 20\%$ relative to nadir

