7.1.2.6.7 Overall Response

Overall response will be determined based on RECIST 1.1 criteria and by irRECIST criteria. The differences are noted below in [Table 12](#). Overall response according to irRECIST is derived from the responses in measurable lesions (based on TMTB) and the presence of any non-measurable lesions.

Table 12 Tumor Response Evaluation: Comparison of RECIST 1.1 and irRECIST

Criteria	RECIST1.1	irRECIST
New measurable lesions (≥ 10 mm)	Always represents PD	Incorporated into tumor burden

New non-measurable lesions (< 10 mm)	Always represents PD	Does not define progression but precludes irCR
Non-Target lesions	Changes contribute to defining BOR of CR, PR, SD, and PD	Contribute to defining irCR (complete disappearance required)
CR	Disappearance of all lesions	Disappearance of all lesions
PR	≥ 30% decrease in the sum of the longest diameter of all target lesions compared with baseline, in absence of new lesions or unequivocal progression of non-target lesions	≥ 30% decrease in tumor burden compared with baseline
SD	Neither sufficient shrinkage to qualify for PR nor sufficient increase to qualify for PD, taking as reference the smallest sum diameters while on study	Neither a 30% decrease in tumor burden compared with baseline nor a 20% increase compared with nadir can be established
PD	At least 20% increase in sum of diameters of target lesions, taking as reference the smallest sum on study. In addition to the relative increase of 20%, the sum must also demonstrate an absolute increase of at least 5mm. The appearance of one or more new lesions is also considered progression.	At least 20% increase in tumor burden compared with nadir (at any single time point) ^a

irRECIST = immune-related Response Evaluation Criteria in Solid Tumors; BOR = best overall response; CR = complete response; irCR = immune-related complete response; PD = progressive disease; PR = partial response; SD = stable disease;

^a Subjects with an initial finding of progressive disease (irPD) before or at the 12-week imaging assessment, but without rapid clinical deterioration, require confirmation of irPD with a second, consecutive scan obtained ≥ 4 weeks from the initiation documentation. Subjects will continue to receive study treatment until irPD is confirmed at this later time point. BOR will therefore include responses occurring at any time before disease progression and after early progression (i.e., within the first 12 weeks of the study).

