7.1.2.6.8 Best Overall Response (RECIST 1.1)

The best overall response is the best response recorded from the start of the study treatment until the end of treatment taking into account any requirement for confirmation. The subject's best overall response assignment will depend on the findings of both target and non-target disease and will also take into consideration the appearance of new lesions [Table 13](#).

Table 13 Best Overall Response (RECIST 1.1)

Target Lesions		Non-Target Lesions		Overall Response
Baseline (Index) and New Measurable Lesions		Baseline Lesions	Unequivocal New Lesions	
CR	CR	CR	No	CR

Target Lesions		Non-Target Lesions		
Baseline (Index) and New Measurable Lesions		Baseline Lesions	Uequivocal New Lesions	Overall Response
CR	Non-CR/Non-PD		No	PR
CR	NE		No	PR
PR	Non-PD or NE		No	PR
SD	Non-PD or NE		No	SD
Not all evaluated	Non-PD		No	NE
PD	Any		Yes or No	PD
Any	PD		Yes or No	PD
Any	Any		Yes	PD

The immune-related best overall response (irBOR) is the best irCR overall response over the study as a whole, recorded between the date of first dose until the last TA prior to subsequent therapy (including tumor resection surgery) for the individual subject in the study (Table 14). As with the primary definitions of tumor response, early progression (i.e., irPD occurring prior to Week 12) will not preclude an irBOR of irCR, irPR or irSD resulting from the Week 12 assessment. An assessment of irPD at or after Week 12 will preclude a subsequent irBOR of irCR, irPR or irSD. However, any post-progression clinical activity in subjects with irBOR of irPD may be summarized for exploratory purposes.

Table 14 Immune-Related Best Overall Response (irBOR)

Target Lesions Baseline (Index) and New Measurable Lesions		Non-Target Lesions ^a		
Total Measurable Tumor Burden (TMTB)		Baseline Lesions	Uequivocal New Lesions	irRC Overall Response
irCR	irCR		No	irCR
irCR	irSD		No	irPR
irPR	irCR or irSD		No	irPR
irSD	irCR or irSD		No	irSD
irPD	Any		Yes or No	irPD
Any	Uequivocal Progression		Yes or No	irPD

Target Lesions Baseline (Index) and New Measurable Lesions		Non-Target Lesions ^a	
Total Measurable Tumor Burden (TMTB)		Baseline Lesions	Uequivocal New Lesions
Any	Any	Yes	irPD

irCR = immune-related complete response; irPR = immune-related partial response; irSD = immune-related stable disease; irPD = immune-related progressive disease

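### Table 14 makes any unequivocal new lesion irPD, against the irRECIST text and Table 12, so the irRECIST category of some subjects with new lesions is undetermined

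*Combined protocol and SAP*

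**What the plan says.** **irRECIST, text and Table 12.** Section 7.1.2.6.4 states: "New measurable lesions do not necessarily constitute progressive disease and they should be added into the total tumor burden". For new lesions too small or otherwise unsuitable to measure it states: "New non-measurable lesions do not constitute disease progression but will prevent the determination of an irCR". irPD on measurable disease is a rise in TMTB of at least 20% from nadir. Section 7.1.2.6.6 repeats that new non-measurable lesions rule out irCR and do not necessarily mean irPD. The irRECIST column of Table 12 says of them: "Does not define progression but precludes irCR".

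**irRECIST, Table 14 (Section 7.1.2.6.8).** The first column is TMTB, headed as covering baseline and new measurable lesions. A further column is headed "Uequivocal New Lesions". Every row that ends in irCR, irPR or irSD has No in that column. The last row reads Any, Any, Yes and ends in irPD. Footnote a says that more or larger non-measurable lesions need not mean irPD, and that equivocal findings count as irSD.

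**RECIST 1.1.** The lead-in of Section 7.1.2.6.3 builds TMTB from target and new lesions and says "the response in target and new measurable lesions is defined based on the change in TMTB (after ruling out irPD"). Its CR, PR, SD and PD definitions then use the target lesions or their sum, and a note makes any new lesion progression. The Table 13 header also includes new measurable lesions. On the time window, Section 7.1.2.6.8 says: "The best overall response is the best response recorded from the start of the study treatment until the end of treatment". Section 7.1.2.6.9 allows treatment to continue after radiologic progression.

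**Measurability.** Section 7.1.2.6.1 sets the measurable threshold at 5 mm for spiral CT or MRI, then defines small non-measurable lesions as "those with all measurements <10 mm with spiral CT or <5 mm with MRI".

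**The concern.** Two sets of criteria are used so that immune-related patterns of response can be told apart from conventional progression. How each set treats a new lesion is the main difference between them. Table 14 is the table from which best overall response would be derived, and on new lesions it applies the RECIST 1.1 rule under an irRECIST label.

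Three results depend on which passage is followed: the irRECIST response rate, the irRECIST progression date, and duration of response, which Section 8.2.4 starts at the first irCR or irPR. The secondary objective in Section 3.2 is to use the activity and PFS signal to design a randomized Phase 2 trial. In an open-label study, choosing between text and table after the scans have been seen is discretion that can be avoided.

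New non-measurable lesions are not remote in this population. Section 7.1.2.6.1 classes bone lesions as non-measurable, and new bone lesions are one of the entry criteria in Section 5.1.2.

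**Working it through.** The plan gives no figure to reproduce. The check applies each rule to the same hypothetical subjects and compares the categories.

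**Setup (assumed for illustration).** Target sum is 100 mm at baseline, which is also the nadir before the scan. Baseline non-target lesions have resolved. TMTB = target sum + new measurable lesions.

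**Rules.**
- irRECIST text (7.1.2.6.4): irPD if TMTB ≥ 1.2 × nadir = 120 mm; irPR if TMTB ≤ 0.7 × baseline = 70 mm; otherwise irSD. New non-measurable lesions only rule out irCR.
- Table 14: irPD if there is any unequivocal new lesion; otherwise as the text.
- RECIST 1.1 definitions with the new-lesion note, and separately the TMTB lead-in of 7.1.2.6.3 read alone.

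| Case | Targets (mm) | New lesion | TMTB (change) | irRECIST text | Table 14 | RECIST 1.1 definitions and note | TMTB lead-in alone |
|---|---|---|---|---|---|---|---|
| A | 50 | 12 mm | 62 (−38%) | irPR | irPD | PD | PR |
| B | 60 | non-measurable | 60 (−40%) | irPR | irPD | PD | PR |
| C | 90 | 12 mm | 102 (+2%) | irSD | irPD | PD | SD |
| D | 95 | non-measurable | 95 (−5%) | irSD | irPD | PD | SD |
| E | 100 | 25 mm | 125 (+25%) | irPD | irPD | PD | PD |
| F | 60 | none | 60 (−40%) | irPR | irPR | PR | PR |

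**irRECIST.** Without a new lesion (F) the last row of Table 14 does not apply, so text and table agree. With a new lesion and TMTB up by 20% or more (E) they also agree. The conflict is confined to cases such as A to D: an unequivocal new lesion, TMTB growth below 20%, and no unequivocal non-target progression.

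**Can Table 14 be read another way?** Its new-lesion column sits under the non-target heading, so it might mean new non-measurable lesions only. That would remove A and C. B and D would remain, in direct conflict with the sentence on new non-measurable lesions in 7.1.2.6.4. On the wider reading, the TMTB column counts new measurable lesions that the last row has already made irPD.

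**RECIST 1.1.** The lead-in alone would call A a PR and C an SD. The section's own note, Section 7.1.2.6.5, Table 12 and Table 13 all make a new lesion PD. Without a new lesion, TMTB equals the target sum and the categories match. One answer therefore survives, and the lead-in is stray wording.

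**Size.** Section 5.2.1.1.3 plans about 30 subjects at the RP2D, and Section 8.2.4 divides responses by treated subjects. One subject moved between irPR and irPD shifts the rate by 1/30 = 3.3 points, two by 2/30 = 6.7, three by 3/30 = 10.0. How many would move is not in the documents.

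**Measurability.** A lesion of 5 to 9 mm on spiral CT meets the 5 mm threshold in one sentence of 7.1.2.6.1 and falls below the 10 mm threshold in the next. Sections 7.1.2.6.4 and 7.1.2.6.6 and Table 12 use 10 mm for new lesions. The slice guidance in 7.1.2.6 (diameter at least twice a 5 mm reconstruction) also gives 2 × 5 = 10 mm.

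**The case against.** The best defence is that the conflict is narrow and partly softened. Footnote a sends small or uncertain findings to irSD, so only unequivocal new lesions are affected. Even under Table 14, irRECIST stays distinct from RECIST 1.1: early irPD needs a confirming scan, and irPD before Week 12 does not bar a better response resulting from the Week 12 assessment. This stands, and it limits the number of subjects concerned. It does not settle which category they get.

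A second defence is that Section 7.1.2.6.6 itself defines irPD by unequivocal increases in the number or size of non-target lesions, and Section 7.1.2.6.2 places all non-measurable disease among the non-target lesions. A reader might infer that, under the text, a new bone lesion can never define irPD by itself. The documents do not support so absolute a reading, and Section 7.1.2.6 assesses bone scans primarily by PCWG2. Cases B and D thus depend on how that clause applies to new lesions. Case A does not: its lesion is measurable, and the text handles it through TMTB.

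On the RECIST 1.1 window, the sentence goes on to mention confirmation requirements, and the Table 12 footnote that admits responses after early progression is attached to the irRECIST cell. That suggests RECIST 1.1 was not meant to count them. Still, no sentence ends RECIST 1.1 best response at first PD.

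It is also fair that the primary objectives are safety and RP2D selection, and that Section 8.1 rules out inferential analysis.

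**Conclusion.** The contradiction is real and should be fixed. Table 14 conflicts with Sections 7.1.2.6.4 and 7.1.2.6.6 and with Table 12 on new lesions. It leaves irRECIST undetermined for subjects with an unequivocal new lesion, TMTB growth under 20% from nadir and no unequivocal non-target progression. Each subject moved between irPR and irPD changes the response rate by about 3.3 points, assuming 30 treated at the RP2D, and changes who enters duration of response. Progression dates change as well. No sample size, error rate or RP2D rule is affected.

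The RECIST 1.1 wording, the Table 13 header, the open end of RECIST 1.1 best response and the two spiral-CT thresholds are lesser drafting conflicts.

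Three stronger conclusions might be inferred and are not supported:
- That neither set of criteria can be applied. RECIST 1.1 gives one answer on new lesions, and irRECIST is unclear only in the subgroup above.
- That the effect on median PFS can be stated in months. The documents give neither a median nor the share of progressions due to new lesions alone.
- That irPD is defective because it has no minimum absolute growth. The plan states this rule consistently, so it is a design choice.

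**What to change.** For the analysis:
- Bring the new-lesion column and last row of Table 14 into line with Sections 7.1.2.6.4 and 7.1.2.6.6 and Table 12: new measurable lesions act through TMTB, and new non-measurable lesions preclude irCR without defining irPD. Name the category given when they preclude irCR.
- State how the clause in 7.1.2.6.6 on unequivocal increases in the number of non-target lesions applies to new lesions.
- Remove the TMTB and irPD wording from 7.1.2.6.3, and new measurable lesions from the Table 13 header.
- End RECIST 1.1 best overall response at the first RECIST 1.1 PD.
- Use one measurability threshold at baseline and follow-up.

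Section 7.1.2.6.4 also ties continued treatment to confirmation of irPD. The sponsor must reconcile the same passages for that use; no stopping rule is proposed here.

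The cost is protocol and SAP wording plus re-derivation of responses from measurements already collected, ideally before any irRECIST result is tabulated. No new scans are needed. One limit remains: Section 7.1.5.3 continues imaging only for subjects who stop for reasons other than progression. If a site stopped treatment on the Table 14 reading, that subject's later course cannot be recovered, and such cases should be listed.
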